6.3 MRD Evaluable Analysis Set

The MRD Evaluable Analysis Set includes all enrolled subjects with measurable MRD status at baseline and at least 1 measurable MRD status postbaseline (subjects who don't have measurable MRD status due to technical issues will be excluded), who received at least 1 dose of carfilzomib. The MRD sensitivity analysis will be based on MRD Evaluable Analysis Set.

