The study is an open-label, phase 2 trial. Subjects may receive treatment until progression. Myeloma disease status will be monitored locally for response and progression per International Myeloma Working Group (IMWG) criteria (Kumar et al, 2016) every 28 ± 7 days from cycle 1 day 1 until confirmed progressive disease (PD), death, lost to follow-up, or withdrawal of full consent (whichever occurs first), regardless of cycle duration, dose delays or treatment discontinuation. Subjects with a suspected CR or better will have a bone marrow for minimal residual disease (MRD) assessment at 12 and 24 months (\pm 4 weeks) from start of treatment (unless a MRD assessment was performed within 4 months before planned assessment). Subjects who end study drug(s) without confirmed PD are required to complete disease response assessments and report new antimyeloma treatment every 28 ± 7 days until first subsequent antimyeloma treatment, death, lost to follow-up, withdrawal of full consent, confirmed PD, or end of study, whichever occurs first. Subjects who discontinue treatment and either start new antimyeloma treatment or have PD, will enter long-term follow-up every 12 weeks until death or end of study.

Number of Subjects

According to Protocol Amendment 3, approximately 85 subjects will be enrolled in the study, with approximately one-third of subjects in first relapse and two-thirds in second relapse. **In late 2021, enrollment was discontinued after 54 subjects were enrolled.**

Summary of Subject Eligibility Criteria

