Bone marrow aspirates will be collected as clinically indicated to confirm a response of complete response (CR) or stringent complete response (sCR). Subjects with a suspected CR or better will have a bone marrow for MRD assessment at 12 months \pm 4 weeks unless a minimal residual disease (MRD) assessment was performed within 4 months prior to the scheduled assessment (eg, coordinated with a bone marrow procedure to confirm CR). Subjects with a MRD[-]CR at the first time point (8 to 12 months from initiation of treatment) should have the subsequent MRD assessment 12 months \pm 4 weeks after the earlier assessment (20-24 months after the start of treatment), if subjects have not relapsed nor started new antimyeloma therapy prior to this subsequent MRD assessment.

Subjects who discontinue either carfilzomib or pomalidomide, but not both drugs, will be considered to remain on study treatment.

Safety laboratory studies (complete blood counts and differential, complete metabolic panel) will be collected on day 1 of each cycle, prior to dosing. A Data Review Team (DRT) will convene regularly to independently evaluate safety. Timing and frequency of the DRT meetings will be detailed in the DRT charter. After discontinuation of study treatment, a safety follow-up visit will be scheduled 30 (+3) days after the last dose of study treatment. Subjects who discontinue treatment and either start new antimyeloma treatment or have PD, will enter long-term follow-up every 12 weeks until death or end of study.

The overall study design is described by a study schema in Section 2.1. The endpoints are defined in Section 4.1.

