9.2.2.2 Bone Marrow Sample Evaluation Including FISH and MRD[-]CR Assessment

A baseline bone marrow aspirate sample will be collected at screening, or prior to dosing at cycle 1 day 1. A bone marrow sample obtained as standard of care may be used as the baseline sample if taken within 45 days prior to enrollment for FISH and MRD testing. The first sample obtained for baseline bone marrow aspirate will be for tumor specific sequence identification for MRD measurement by next-generation sequencing (NGS) at the central lab.

After screening, bone marrow aspirate will be obtained:

- at time of suspected CR or better. Depending on when this procedure occurs, an additional aliquot of bone marrow aspirate will be frozen and saved at the central lab for MRD testing to be performed at a later time.
- at time of MRD assessment. MRD will be conducted in subjects with suspected CR or better at 12 months (\pm 4 weeks) but may be performed as early as 8 months after start of treatment in subjects with suspected CR or better. Subjects with a MRD[-]CR response at the first time point should have the subsequent MRD assessment 12 months \pm 4 weeks after the earlier assessment, if subjects have not relapsed nor started new antimyeloma therapy prior to this subsequent MRD assessment.

If the bone marrow aspirate sample taken is found to be of insufficient quantity or quality for testing, the site may be contacted to request provision of a suitable archival bone marrow aspirate sample.

9.2.2.3 Bone Lesion Assessment (Skeletal Survey, Computed Tomography [CT], or Positron Emission Tomography/CT [PET/CT])

Skeletal survey will include lateral radiograph of the skull, anteroposterior and lateral views of the spine, and anteroposterior views of the pelvis, ribs, femora, and humeri. Low-dose whole body computed tomography or fluorodeoxyglucose-positron emission tomography/computed tomography (FDG-PET/CT) may be used in place of skeletal survey. Bone lesion assessment at screening (all subjects) may be done within 28 days prior to enrollment, if performed as a part of standard of care. It should be repeated if worsening clinical symptoms suggest PD or as clinically indicated. The same method of

assessment used at baseline will be used throughout the study. These imaging studies will be read locally.

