10.2 Analysis Sets, Subgroups, and Covariates

10.2.1 Analysis Sets

Safety Analysis Set

The Safety Analysis Set includes all enrolled subjects who received at least 1 dose of carfilzomib. The analysis of efficacy and safety analyses will be based on the Safety Analysis Set.

MRD Evaluable Analysis Set

The MRD Evaluable Analysis Set includes all enrolled subjects with measurable MRD status at baseline and at least 1 measurable MRD status post baseline (subjects who don't have measurable MRD status due to technical issues will be excluded), who received at least 1 dose of carfilzomib. The MRD sensitivity analysis will be based on MRD Evaluable Analysis Set.

Pharmacokinetic Analysis Set

The PK Analysis Set will include a subset of up to 20 evaluable subjects in Safety Analysis Set, who have participated in the PK assessment. Evaluable subjects are defined as those subjects providing sufficient PK samples to permit estimation of PK parameters on cycle 2 day 1.

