3.1 Study Design

The study is an open-label, phase 2 trial treating subjects with first or second relapse of multiple myeloma who were refractory to prior lenalidomide treatment and may have been exposed to prior daratumumab **or other anti-CD38 antibody therapy**. Based on available information for this study population, **the reference rate listed in the protocol section 4.2 indicates the ORR was considered to be 60%, while for MRD[-]CR was considered to be 3%.**

Subjects may receive treatment until progression. Myeloma disease status will be monitored locally for response and progression per International Myeloma Working Group (IMWG) criteria (Kumar et al, 2016) every 28 ± 7 days from cycle 1 day 1 until

confirmed progressive disease (PD), death, lost to follow-up, or withdrawal of full consent (whichever occurs first), regardless of cycle duration, dose delays or treatment discontinuation.

Subjects with a suspected CR or better will have a bone marrow for minimal residual disease (MRD) assessment at 12 and 24 months (\pm 4 weeks) from start of treatment (unless an MRD assessment was performed within 4 months before planned assessment).

Subjects who end study drug(s) without confirmed PD are required to complete disease response assessments and report new antimyeloma treatment every 28 ± 7 days until first subsequent antimyeloma treatment, death, lost to follow-up, withdrawal of full consent, confirmed PD, or end of study, whichever occurs first. Subjects, who discontinue treatment and either start new antimyeloma treatment or have PD, will enter long-term follow-up every 12 weeks until death or end of study.

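### The MRD-evaluable sensitivity analysis of 12-month MRD[-]CR drops treated subjects who never reached suspected CR, although they are known failures, and so inflates the rate by about 52/m.

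*SAP*

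**What the plan says.** SAP 6.3 builds the MRD Evaluable Analysis Set from "all enrolled subjects with measurable MRD status at baseline and at least 1 measurable MRD status postbaseline", limited to subjects who received carfilzomib. A parenthesis adds that "subjects who don't have measurable MRD status due to technical issues will be excluded". Protocol 10.2.1 sets the same condition: "measurable MRD status at baseline and at least 1 measurable MRD status post baseline".

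Protocol 9.2.2.2 says who is sampled: "MRD will be conducted in subjects with suspected CR or better at 12 months", with sampling allowed from month 8. SAP 3.1 agrees: "Subjects with a suspected CR or better will have a bone marrow for minimal residual disease (MRD) assessment". The protocol synopsis, Protocol 5.1 and the MRD marrow row of the Schedule of Activities say the same.

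Two places are looser. The biomarker row of the Schedule of Activities ties the blood sample to an MRD marrow taken at suspected CR or better and/or at 12 and 24 months. The any-time MRD[-] rate (Protocol 10.4.2.2, SAP 5) refers to samples from subjects with very good partial response (VGPR) or better.

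The main 12-month MRD[-]CR rate divides by all subjects who received carfilzomib. Protocol 10.4.2.2, SAP 5 and SAP Table 9-2 name the MRD Evaluable Analysis Set for a sensitivity analysis of it, using the same exact method.

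**The concern.** MRD[-]CR requires CR. A treated subject who never reaches suspected CR is therefore a known failure for this endpoint, not a subject with missing data. The main analysis counts that subject in its denominator. The sensitivity set removes the same subject, because the clinical failure is the reason no marrow was scheduled. Exclusion then depends on the outcome.

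At stake is how a named sensitivity analysis of the key secondary endpoint will be read. The parenthesis suggests a set that allows for assay problems. What would be reported is closer to a rate among subjects who came near CR, without a label saying so.

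**Working it through.** **Inputs.** Treated subjects: 52 (Protocol 10.1, SAP 3.2). Reference rate 3% and alternatives 10% and 12% (Protocol Table 10-1, SAP Table 3-1). Method: Clopper-Pearson, two-sided 90%. The evaluable count m is not in the documents, so every value below is an assumption.

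**The plan's own figures.** With n = 52, the smallest count whose 90% lower limit exceeds 3% is 5. The attained one-sided error is 0.0196, and power is 76.3% at a true 12% and 60.5% at 10%, as tabled. The synopsis interval of 0.055 to 0.221 also reproduces, using 0.12 × 52 = 6.24 as the count.

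**Numerator.** Let x be the number of MRD[-]CR subjects. Each has a post-baseline sequencing result. Protocol 9.2.2.2 uses the baseline aspirate to identify the tumour sequence that is later tracked, which implies that each also has a measurable baseline. On that condition x is the same in both analyses.

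**Ratio.** (x/m) ÷ (x/52) = 52/m, for x above 0.

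**Illustration.** Take x = 6, the whole number nearest 6.24. The values 39 and 42 are 0.75 × 52 and 0.80 × 52 = 41.6 rounded up. They show what m would be if as many subjects were sampled as respond in the plan's ORR scenarios.

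| m (assumed, except 52) | 52/m | 6/m | 90% exact interval |
|---|---|---|---|
| 52 (main analysis) | 1.00 | 11.5% | 5.1% to 21.5% |
| 42 | 1.24 | 14.3% | 6.4% to 26.3% |
| 39 | 1.33 | 15.4% | 6.9% to 28.1% |
| 26 | 2.00 | 23.1% | 10.6% to 40.5% |
| 20 | 2.60 | 30.0% | 14.0% to 50.8% |

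**Separating technical failures from non-response.** Assume 5 technical exclusions. Removing only those gives 6/47 = 12.8%, a factor of 52/47 = 1.11. The further step from 47 to m comes from dropping subjects for lack of a marrow: 47/42 = 1.12, 47/39 = 1.21, 47/26 = 1.81 and 47/20 = 2.35.

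**If the baseline condition fails.** If one of the 6 lacked a measurable baseline, the evaluable rate would be 5/m. That is below 11.5% only when m is 44 or more (5/43 = 11.6%, 5/44 = 11.4%).

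**The case against.** The strongest reply is that the parenthesis in SAP 6.3 shows the intent to exclude only technical failures, so this is a matter of clarification. That may be the intent. But the sentence separately requires a post-baseline result, and a programmer who applies it literally will drop subjects never sampled for want of response.

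A second reply is that more subjects than those at suspected CR may be sampled. This stands in part. The biomarker row and the VGPR wording allow for it, and a locally suspected CR that the IRC does not confirm also enters m. These raise m and shrink the ratio; they do not reverse it.

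A reader might infer four stronger things, none of which the documents support:

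- **That the fault is an analysis that can never fall below the main rate.** Any set that removes only subjects who cannot be counted as MRD[-]CR behaves this way against an all-treated denominator, including the one proposed below (12.8% against 11.5% above). The fault is the removal of known failures.
- **That the plan's ORR scenarios cap m at 39 or 42.** ORR is IRC-confirmed, whereas marrow is triggered by suspected CR under local monitoring. The cap is an assumption.
- **That the key secondary conclusion is at risk.** The gated comparison with 3% uses the Safety Analysis Set, and no section compares the MRD Evaluable Analysis Set with 3%.
- **That the same argument covers the any-time MRD[-] rate.** There, an unsampled subject in VGPR has unknown status and is not a known failure.

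**Conclusion.** The concern holds in a limited form. Read literally, the set excludes treated subjects because they did not reach suspected CR, and this raises the 12-month MRD[-]CR sensitivity rate by about 52/m. That is more than technical failures alone would cause, by an amount set by how many subjects were never sampled: modest if m is near 42, large if m is near 20.

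The size rests on an unknown m, and the constant numerator rests on a measurable baseline for every MRD[-]CR subject, which Protocol 9.2.2.2 implies but no rule states. The investigator, ORCA, per-protocol and modified-safety sensitivity analyses in SAP Table 9-2 do not share the problem. The change is worth making because it concerns a named analysis of the key secondary endpoint and is cheap.

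**What to change.** For the 12-month MRD[-]CR sensitivity analysis only, define a separate set: the Safety Analysis Set minus subjects with no identifiable baseline clone or with a documented technical MRD failure. Count subjects not sampled because they never reached suspected CR as not MRD[-]CR. State that this rate can still only equal or exceed the all-treated rate. If a rate among sampled subjects is also shown, label it as conditional on sampling and give m.

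Do not rewrite SAP 6.3 globally. The existing set also serves the other MRD endpoints in Table 9-2 and the PFS-by-MRD analyses in SAP 9.5.3. A global change would place unsampled subjects of unknown MRD status in the group recorded there as not achieving MRD[-].

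Reconcile the biomarker row and the VGPR-or-better wording with the suspected-CR schedule.

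The cost is wording in the SAP, with an entry in SAP 10 as a change from the protocol, and one extra set to program. No new samples are needed. The sponsor would report a less favourable sensitivity rate.

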6.4 Modified Safety Analysis Set

The modified safety analysis set (mSAS) will be used in the sensitivity analysis for primary endpoint and key secondary endpoints, and other efficacy endpoints including PFS, OS, and CR in order to adjust for the COVID-19 impact on the Safety Analysis Set population. The mSAS is a subset of Safety Analysis Set excluding subjects who are impacted by COVID-19.

The COVID-19 impact refers to:

- (1) any COVID-19 adverse events which are identified using the COVID-19 Standardized MedDRA Query (SMQ) narrow search strategy, and COVID-19 events collected on the Confirmed COVID-19 Status CRF;**
- (2) the reason for Investigational Product (IP)/Non-IP Dose Change/Withheld/Dose Delay is COVID-19 control measures recorded on the CRFs for IP Administration and Non-IP Administration;**
- (3) the reason for ending IP/Non-IP is COVID-19 control measures recorded on CRFs for End of IP Administration and End of Non-IP Administration;**
- (4) important protocol deviations (IPDs) related to COVID-19 control measures;**
- (5) COVID-19 related protocol deviation: 940 series, 950 series and 960 series of protocol deviation codes in the study IPD list.**

6.5 Per Protocol Set(s)

The per protocol analysis set is a subset of the safety analysis set which includes subjects who do not have important protocol deviations that might affect the interpretation of the analyses of the efficacy endpoints. Subjects with the following protocol deviations will be excluded from the per protocol set:

Major inclusion criteria not met:

- 103 – First or Second Relapse
- 104 – Refractory to Lenalidomide
- 106 – Measurable Disease
- 107 – Prior Therapy Response
- 108 – Prior Carfilzomib Response
- 109 – ECOG

Major exclusion criteria met:

- 201 – Primary Refractory
- 202 – Waldenström macroglobulinemia
- 203 – Multiple myeloma of IgM subtype
- 204 – POEMS syndrome
- 205 – Plasma cell leukemia
- 206 – Primary amyloidosis
- 207 – Amyloidosis associated with myeloma
- 208 – Myelodysplastic syndrome
- 209 – Toxicity with lenalidomide therapy
- 210 – Prior treatment with pomalidomide
- 211 – History of other malignancy within past 3 years
- 212 – Active hepatitis B virus infection
- 213 – HIV or hepatitis C infection
- 214 – Graft vs host disease
- 215 – Cirrhosis
- 216 – Uncontrolled hypertension
- 217 – Impaired cardiac function within 4 months
- 218 – Intolerance to hydration

Major treatment non-compliance

- 501 – Incorrect carfilzomib dose (over dose)
- 502 – Incorrect carfilzomib dose (under dose)
- 503 – Carfilzomib dose not adjusted per protocol
- 504 – Carfilzomib not reduced for 1 cycle before re-escalation
- 505 – Carfilzomib insufficient infusion time
- 506 – Carfilzomib dose off schedule
- 507 – Pomalidomide not administered per protocol
- 508 – Pomalidomide not withheld per protocol
- 509 – Dexamethasone not administered per protocol
- 510 – Compromised IP

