- 213 Known human immunodeficiency virus (HIV) infection, hepatitis C infection (subjects with hepatitis C that achieve a sustained virologic response after antiviral therapy are allowed). Tests to be performed if required per local country regulations.
- 214 Presence of graft-versus-host disease including continuation of immunosuppressive therapy despite resolution of graft-versus-host disease
- 215 Known cirrhosis
- 216 Uncontrolled hypertension, defined as an average systolic blood pressure ≥ 160 mmHg or diastolic ≥ 100 mmHg despite optimal treatment (measured following European Society of Hypertension/European Society of Cardiology 2018 guidelines; Section 12.10). Subjects with controlled hypertension as defined by the guidelines (link available in Section 12.10) are eligible.
- 217 Active congestive heart failure (New York Heart Association Class III to IV), symptomatic ischemia, uncontrolled arrhythmias, screening ECG with corrected QT interval (QTc) of > 470 msec, pericardial disease, or myocardial infarction within 4 months prior to enrollment
- 218 Intolerance to hydration due to pre-existing pulmonary or cardiac impairment
- 219 History of interstitial lung disease or ongoing interstitial lung disease
- 220 Active infection within 14 days prior to enrollment requiring systemic antibiotics, antiviral (except antiviral therapy directed at hepatitis B) or antifungal agents. Such infection must be fully resolved prior to initiating study treatment.
- 221 Significant neuropathy (grades 3 to 4, or grade 2 with pain) within 14 days prior to enrollment
- 222 Known pulmonary hypertension
- 223 Pleural effusions requiring thoracentesis or ascites requiring paracentesis within 14 days prior to enrollment

Prior/Concomitant Therapy

- 224 Immunotherapy with potential antimyeloma activity within 21 days prior to enrollment
- 225 Monoclonal antibody therapy within 21 days prior to enrollment
- 226 Chemotherapy with approved anticancer therapeutic within 21 days prior to enrollment
- 227 Plasmapheresis within 21 days prior to enrollment
- 228 Glucocorticoid therapy within 14 days prior to enrollment that exceeds a cumulative dose of 160 mg of dexamethasone or equivalent dose of other corticosteroids
- 229 Focal radiation therapy within 7 days prior to enrollment. Radiation therapy to an extended field involving a significant volume of bone marrow within 21 days prior to enrollment (ie, prior radiation must have been to < 30% of the bone marrow)

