- 230 Major surgery (except kyphoplasty) within 28 days prior to enrollment
- 231 Autologous or allogeneic stem cell transplant within 90 days prior to enrollment

Prior/Concurrent Clinical Study Experience

- 232 Currently receiving treatment in another investigational device or drug study, or less than 28 days since ending treatment on another investigational device or drug study(ies). Other investigational procedures while participating in this study are excluded.

Diagnostic Assessments

- 233 Calculated or measured creatinine clearance < 30 mL/min (calculation must be based on the Cockcroft and Gault formula) within 28 days prior to enrollment
- 234 Hepatic dysfunction within 28 days prior to enrollment:
 - bilirubin > 1.5 x the upper limit of normal (ULN)
 - aspartate aminotransferase (AST) or alanine aminotransferase (ALT) > 3 x ULN
- 235 Left ventricular ejection fraction < 40% assessed by transthoracic ECHO
- 236 Absolute neutrophil count (ANC) < $1 \times 10^9/L$ within 28 days prior to enrollment. Screening ANC should be independent of granulocyte- and granulocyte macrophage-colony stimulating factor support for at least 1 week and of pegylated granulocyte stimulating factor for ≥ 2 weeks
- 237 Hemoglobin < 80 g/L within 28 days prior to enrollment. Subjects should not have received red blood cell (RBC transfusions) for at least 7 days prior to obtaining the screening hemoglobin.
- 238 Platelet count < $50 \times 10^9/L$ ($\leq 30 \times 10^9/L$ if plasma cell percentage in the bone marrow is $\geq 50\%$) within 28 days prior to start of treatment

Subjects should not have received platelet transfusions for at least 7 days prior to obtaining the screening platelet count.

Other Exclusions

- 239 Pregnant or breastfeeding female subjects or female subjects who are planning to become pregnant or breastfeed during treatment and for an additional 30 days after the last dose of carfilzomib or pomalidomide (whichever occurs latest).
- 240 Female subjects of childbearing potential unwilling to use 2 methods of contraception (1 of which must be highly effective; see Section 12.5) during the study and for an additional 30 days after the last dose of carfilzomib or pomalidomide (whichever occurs latest). Additionally, subjects unwilling to use contraception at least 28 days prior to initiating treatment. Refer to Section 12.5 for additional contraceptive information.

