7.1.7.4 Prohibited Therapies

Use of the treatments listed below is prohibited during the study:

- Subjects may not receive treatment with an investigational drug or device while participating in this study
- During cycle 1, the prophylactic use of hematopoietic growth factors is prohibited
- Other agents that target CD38
- Medications used for other indications that have antimyeloma properties (for example, interferon and clarithromycin (Ghosh et al, 2014))
- Administration of approved or investigational treatments for multiple myeloma (including but not limited to conventional chemotherapies, IMiDs, or proteasome inhibitors other than those agents that are part of the regimen for which the subject was enrolled)
- Concomitant administration of investigational agents is prohibited. Administration of commercially available agents with activity against or under investigation for multiple myeloma are not permitted

Continuation of study drug during or after emergency orthopedic surgery or radiotherapy because of subject benefit may only occur in the absence of disease progression and after consultation with and approval by the sponsor. Such emergency radiotherapy may consist of localized radiotherapy for pain control or for stabilization of an extensive bone lesion at high risk of pathologic fracture or damage to surrounding tissues in a subject in whom delay of systemic therapy is not appropriate. Such radiotherapy is to occur within the first 2 cycles of treatment and the absence of evidence of disease progression is to be reviewed and approved by the sponsor.

The sponsor must be notified in advance (or as soon as possible thereafter) of any instances in which prohibited therapies are administered.

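### The per-protocol set's closed list of exclusion-criterion deviations ends at 218 and omits the washout and recent-therapy criteria 224-229, 231 and 232, contrary to the set's own stated purpose

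*SAP*

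**What the plan says.** SAP 6.5 opens with a principle. The per-protocol set is the part of the Safety Analysis Set made up of "subjects who do not have important protocol deviations that might affect the interpretation of the analyses of the efficacy endpoints". The rule that implements it follows: "Subjects with the following protocol deviations will be excluded from the per protocol set". Three groups of codes are then listed:

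- inclusion criteria 103, 104 and 106-109;
- exclusion criteria 201-218, the last entry being "218 – Intolerance to hydration";
- study-drug dosing codes 501-510.

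The list has no 'such as' and no provision for further deviations identified at data review.

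Protocol 6.2 numbers its exclusion criteria 201 to 248. Those after 218 include the whole Prior/Concomitant Therapy block (224-231), for example "Chemotherapy with approved anticancer therapeutic within 21 days prior to enrollment" (226), "Plasmapheresis within 21 days prior to enrollment" (227) and "Autologous or allogeneic stem cell transplant within 90 days prior to enrollment" (231). Criterion 232 (treatment in another investigational study, current or ended less than 28 days before) also falls after 218.

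SAP Tables 9-1 and 9-2 name the per-protocol population as a sensitivity analysis for ORR (primary), 12-month MRD[-]CR (key secondary), PFS, OS and CR rate.

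**The concern.** The list does not follow from the principle. It takes every number from 201 to 218 and stops partway through the Other Medical Conditions heading (211-223). Hypertension and hydration intolerance therefore remove a subject, while chemotherapy, plasmapheresis or a transplant shortly before enrollment do not. The SAP gives no reason for stopping there.

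Response under Protocol Appendix 11 is mainly a percentage fall in serum or urine M-protein, and SAP section 5 takes baseline as the last value before first dose. Treatments given close to enrollment can disturb that comparison in either direction. Residual activity of an earlier drug or steroid could add to a later fall. Plasmapheresis would tend to lower the starting value and make a 50% fall harder to reach.

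A per-protocol analysis exists to show whether such deviations drive the result. If it keeps these subjects, agreement with the main analysis says nothing about them, yet a reader would probably take it as reassurance.

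**Working it through.** **Step 1. Compare the lists (SAP 6.5 against Protocol 6.2).**

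- Exclusion criteria in the protocol: 201-248, so 48.
- On the per-protocol list: 201-218, so 18.
- Not on the list: 219-248, so 48 − 18 = 30.
- Washout or recent-therapy criteria among the 30: 224 immunotherapy, 225 monoclonal antibody, 226 chemotherapy, 227 plasmapheresis (each 21 days), 228 glucocorticoid above 160 mg dexamethasone equivalent in 14 days, 229 radiation (7 or 21 days), 231 transplant (90 days), 232 other investigational treatment (28 days). That is eight.
- Codes 501-510 concern carfilzomib, pomalidomide and dexamethasone dosing and compromised product, so they do not capture these eight.

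**Step 2. Look for another route to exclusion.** SAP 9.3 lets the categories of important deviation be updated until database lock and lists inclusion/exclusion deviations by subject. It does not tie either to per-protocol membership. SAP section 10 repeats the principle only.

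**Step 3. Reproduce the plan's figures.** Inputs: N = 52 treated; references 60% (ORR) and 3% (MRD[-]CR); one-sided alpha 0.05 (Protocol 10.1, SAP 3.2). The exact lower bound for r of n is the 5th percentile of Beta(r, n − r + 1). The smallest r with a bound above the reference is 38 for ORR and 5 for MRD[-]CR.

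- P(X ≥ 38 | 52, 0.80) = 91.8%; at 0.75, 69.2%.
- P(X ≥ 5 | 52, 0.12) = 76.3%; at 0.10, 60.5%.

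All four match SAP Table 3-1.

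**Step 4. Illustrate what excluding deviators could change.** The number of deviators is assumed, because the documents give none.

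| Assumed case | r/n | 90% lower bound | Against reference |
|---|---|---|---|
| ORR, all treated | 38/52 | 0.612 | above 60% |
| ORR, all treated | 37/52 | 0.591 | below |
| 38/52 less one responding deviator | 37/51 | 0.605 | above |
| 38/52 less two responding deviators | 36/50 | 0.597 | below |
| 37/52 less one non-responding deviator | 37/51 | 0.605 | above |
| 39/52 less two responding deviators | 37/50 | 0.619 | above |
| 39/52 less three responding deviators | 36/49 | 0.612 | above |
| MRD[-]CR, all treated | 5/52 | 0.039 | above 3% |
| 5/52 less one MRD-negative deviator | 4/51 | 0.027 | below |

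The ORR reversals need a count at the boundary. Exactly 38 responders has probability 6% if the true ORR is 0.80 and 12% if it is 0.75. Away from the boundary, two or three deviators leave the reading unchanged.

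**The case against.** The best defence is that the opening sentence of 6.5 already covers these subjects: anyone whose deviation might affect efficacy interpretation is out, SAP section 10 restates only that principle, and deviators will be visible in the listings. This shows what was intended, and it means exclusion is not impossible. But the sentence that decides membership names particular codes, and a programmer would implement those codes. If the principle governs, the list contradicts it and the two need reconciling.

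A second defence is that this is one supportive analysis among several, and the pass/fail rule applies only to the Safety Analysis Set. That is correct and limits the weight of the point. The repeat of SPEP, UPEP and SFLC on cycle 1 day 1, unless screening values are within 14 days (Protocol 9.2.2.1), also narrows carry-over at baseline without removing it.

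Some stronger readings are tempting but are not supported:

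- *All prior-treatment criteria are missing.* They are not. Criteria 104, 107, 108, 209 and 210 concern prior treatment and are listed, as is 106 (measurable disease), which bears directly on response.
- *Prohibited antimyeloma drugs on study (Protocol 7.1.7.4) would inflate response unchecked.* Largely not. Protocol 9.2.2.1 and Appendix 11 require two consecutive assessments before any new therapy, and SAP section 5 censors PFS and DOR at new anticancer therapy. OS has no such censoring.
- *The omission favors KPd.* The direction is not fixed, as the plasmapheresis example shows.
- *Criteria 215, 216 and 218 should come off.* That is a preference. The set also serves PFS and OS, where such conditions may matter.

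**Conclusion.** The point holds as a mismatch between the stated purpose of the per-protocol set and its operative list. Run as written, five sensitivity analyses keep any subject who broke 224-229, 231 or 232 and so cannot test robustness to those deviations. The primary analysis, its power and the fixed-sequence rule are untouched.

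The practical size is unknown. It depends on how many such deviations occurred, which the documents do not report and which may be zero. If there are a few and the count lies at the boundary, the per-protocol bound can cross the reference either way; otherwise the effect is small.

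The conclusion rests on two assumptions: that the list is applied literally, and the clinical-statistical judgement that therapy shortly before enrollment can affect M-protein or marrow status around baseline. It is a worthwhile correction to a supportive analysis, not a threat to the main result.

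**What to change.** Before database lock, add 224, 225, 226, 227, 228, 229, 231 and 232 to the major exclusion criteria in SAP 6.5. Keep all current entries, including 215, 216 and 218. Record in the SAP that the change was made without reference to response results. If the sponsor judges that any of the eight does not affect efficacy interpretation, 6.5 should say so and why. A code for prohibited antimyeloma therapy on study is optional, given the confirmation and censoring rules.

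No new data are needed: prior antimyeloma therapy dates are collected (Protocol 7.8.1) and inclusion/exclusion deviations are listed by subject (SAP 9.3). The costs are a slightly smaller per-protocol set and a late change to the SAP of an open-label study. SAP version 3.0 is dated 7 September 2022, after enrollment stopped in late 2021. For that reason the change should only add criteria and should be documented as blind to outcome.
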